6.14.7. Additional Safety Sections

6.14.7.1. Secondary Safety Analyses: In-Clinic Blood Pressure/Pulse Rate

- Day 1 (Visit 3) In-clinic BP and PR change post first dose

Change in in-clinic BP and PR from 0 up to 8 hours post dose measured on the first day of study drug dosing will be analyzed using an MMRM analysis with baseline value, treatment, time post dose (hours) as fixed effects, and treatment by time and baseline by time as interaction terms with repeated measures of time (hour) within subject. Two baselines will be considered: the Visit 3 pretreatment value (Time 0) and the time-matched baseline values from Visit 2 (hourly value 0-6 hours). For the second of these, there is no time-matched value for the Visit 3 7- and 8-hour time points, so these will use the Visit 2 6-hour time point as their baseline value. A separate change from baseline analysis will be completed for each baseline approach.

- Change in in-clinic BP and PR from baseline (Visit 2, predose) up to Week 12 (Visit 11)

To assess the impact of LY3154207 on BP and PR over time, change from baseline in in-clinic BP and PR to Week 12 will be analyzed using MMRM with response variable being the daily average of 0 to 6 hours, with fixed effects for baseline value, treatment, visit, and treatment by visit and baseline by visit as interaction terms with repeated measures of visit within subject. Change from baseline in BP and PR will be assessed at both 6 and 12 weeks. Analysis at 6 weeks will help to evaluate any significant changes (if any) in BP and PR earlier than 12 weeks (end of study) and if they accommodate by 6 weeks.

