10.1. Sample Size Determination

Approximately 750 subjects may be screened in order that 340 subjects are randomized in the study. CCI

If the true effect size for LY3154207 relative to placebo on the CoA is 0.4 with the sample size of 340 there will be over 80% probability of passing this criterion. A 20% discontinuation rate by Week 12 has been accounted for in the sample size determination.

Sample size was estimated based on the work of Wesnes et al. (2005) where the difference in mean change from baseline for rivastigmine compared to placebo and the pooled standard deviation (SD) for CoA were estimated as 5.7 units and 18 units, respectively. The rivastigmine effect corresponding to a reduction in the deficit of subjects compared to age-matched healthy volunteers is approximately 45%. Based on this, the effect size of 0.4 in this study corresponds to a mean difference of 7.2 units (approximately 57% reduction in the deficit).

This sample size will allow for assessment of the in-clinic BP and pulse rate on the first day of dosing in order to evaluate any changes after the first dose of treatment that were observed in Phase 1. If the SD of the in-clinic SBP is assumed to be 15 mmHg, then the difference from the mean to the upper limit of a 95% confidence interval (CI) of the change from baseline of SBP relative to placebo is expected to be <4.7 mmHg. If there is any initial rise in BP or pulse rate, the in-clinic 6- and 12-week assessments along with the HBPM measure will be used to assess if the rise accommodates. The difference from the mean to the upper limit of a 95% CI of the change in average SBP measured at each of these visits relative to placebo is expected to be <3.5 mmHg. This assumes an SD of 10 mmHg and a 20% discontinuation rate.

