
Secondary
 
Safety:
 
To evaluate the effect of LY3154207 on acute changes of vital signs on the first day of dosing
 
To evaluate the effect of LY3154207 on SBP and DBP on the first day of dosing
 
To evaluate the effect of LY3154207 on pulse rate on the first day of dosing
 
To evaluate the effect of LY3154207 on SBP and DBP from baseline to Week 12
 
To evaluate the effect of LY3154207 on pulse rate from baseline to Week 12
 
To evaluate the effect of LY3154207 using HBPM
 
To evaluate the effect of LY3154207 on physical withdrawal symptoms
	
Number of subjects who met the potentially clinically significant vital signs criteria at 3 consecutive time points at Visit 3 (Day 1 stopping rules)
 
Change in in-clinic BP from 0 up to 8 hours post dose on the first day of study drug dosing
 
Change in in-clinic pulse rate from 0 up to 8 hours post dose on the first day of study drug dosing
 
Change in in-clinic mean BP at baseline to mean SBP at Week 12
 
Change in in-clinic mean pulse rate at baseline to mean pulse rate at Week 12
 
Change in HBPM for SBP, DBP, and pulse rate from baseline to Week 12
 
Change in the PWC-20 total score from Week 12 to in-clinic follow-up visit

Pharmacokinetics:
 
To assess the PK of LY3154207 in a population of subjects with mild-to-moderate dementia due to Lewy Body Dementia
	
Steady-state trough plasma concentrations of LY3154207 at Week 12

Objectives and Endpoints

Objectives	Endpoints

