5.2. Determination of Sample Size

Approximately 750 subjects will be screened to achieve 340 randomized subjects. The randomization will be 1:1:1:1 to LY3154207 (10, 30, or 75 mg QD) or placebo treatment arms.

CCI

If the true effect size for LY3154207 relative to placebo on the CoA is 0.4 with the sample size of 340, there will be greater than 80% probability of passing this criterion. A 20% discontinuation rate by Week 12 has been accounted for in the sample size determination.

Sample size estimation was based on an article by Wesnes et al. (2005) where the difference in mean change from baseline for rivastigmine compared to placebo and the pooled standard deviation (SD) for CoA were estimated as 5.7 units and 18 units, respectively. The rivastigmine effect corresponded to a reduction in the deficit of subjects compared to age-matched healthy volunteers of approximately 45%. Based on this result, the effect size of 0.4 in this study corresponds to a mean difference of 7.2 units (approximately 57% reduction in the deficit).

This sample size will allow assessment of the in-clinic blood pressure (BP) and pulse rate (PR) values on the first day of dosing in order to evaluate any changes after the first dose of treatment that was seen in Phase 1. If the SD of the in-clinic systolic blood pressure (SBP) value is assumed to be 15 mm Hg, then the difference from the mean to the upper limit of a 95% confidence interval (CI) of the change from baseline in SBP relative to placebo is expected to be <4.7 mm Hg. If there is any initial rise in BP or PR, the in-clinic 6- and 12-week assessments along with the home blood pressure monitoring (HBPM) and ambulatory blood pressure monitoring (ABPM) measures will be used to assess whether the rise accommodates. The difference from the mean to the upper limit of a 95% CI in the change in average SBP measured at each of these visits relative to placebo is expected to be <3.5 mm Hg. This assumes an SD of 10 mm Hg and a 20% discontinuation rate.

Simulations were conducted in FACTs Version 5.1.1 using a Bayesian normal dynamic linear model (NDLM).

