6.2. General Considerations

Statistical analysis for this study will be the responsibility of Eli Lilly Company (Lilly) or its designee. The statistical analyses performed as part of the interim analyses will be conducted by the designated statistical analysis center, which forms part of the internal assessment committee (IAC) (see Unblinding and Communication Plan for more details).

Analyses will be conducted in SAS Version 9.4 or greater, and Spotfire graphical package will be used to review safety data on an ongoing basis during the trial (for example, for trial level safety reviews). Packages to be used for the analysis of digital biomarker data will be specified in the Digital Biomarker Analysis Plan.

As HBEH is a Phase 2 study, the appropriate estimand is a de jure estimand, where efficacy of LY3154207 is assessed under the paradigm of all subjects taking study drug as intended. Intercurrent events for HBEH are defined to be when subjects discontinue the study prior to completing the 12 weeks of treatment. While subjects are allowed to be on steady doses of symptomatic treatments, the protocol does not allow for subjects to initiate any therapeutic agent that has been demonstrated to be effective for treatment of cognition in LBD during the trial. The primary analyses use a Bayesian mixed-model repeated measures (MMRM) analyses of the CDR-COA to evaluate cognition in subjects with mild-to-moderate LBD compared with placebo. This analysis assumes that the intercurrent events lead to data that is missing at random (MAR).

Unless otherwise specified, all efficacy analyses will be conducted on the Evaluable Patient population (EPP). Analyses will be conducted according to the treatment the subject actually received.

When change from baseline is assessed, subjects will be included in the analysis only if both the baseline and a postbaseline measure are available. Unless otherwise defined, a baseline measure is the last non-missing observation collected prior to the subject receiving study treatment.

Safety analyses will be conducted on the safety analysis set comprising all subjects who received at least 1 dose of study medication. Summary statistics, tabulations, and graphs will be provided as appropriate.

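### Day 1 blood pressure and pulse are analysed in two single-baseline models with no named lead; one model with both baselines would be cheap, usually somewhat more precise, and give one answer

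*SAP*

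**What the plan says.** The secondary safety endpoint in SAP Table HBEH.4.1 is "Change in in-clinic BP from 0 up to 8 hours post dose on the first day of study drug dosing", with a parallel endpoint for pulse rate. SAP 6.14.7.1 specifies an "MMRM analysis with baseline value, treatment, time post dose (hours) as fixed effects", plus treatment-by-time and baseline-by-time interactions. Each model therefore has one baseline term.

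Two baselines are named: the Visit 3 pre-dose value (time 0) and the Visit 2 reading at the matching hour. Visit 2 monitoring stops at 6 hours, so for the 7- and 8-hour readings the SAP says "so these will use the Visit 2 6-hour time point as their baseline value". It then says "A separate change from baseline analysis will be completed for each baseline approach". Protocol 10.3.4.3 and the protocol synopsis describe the same plan.

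Neither document says which of the two results answers the endpoint. The general rule in SAP 6.2 is "Unless otherwise defined, a baseline measure is the last non-missing observation collected prior to the subject receiving study treatment", but SAP 6.14.7.1 does define otherwise, by naming two baselines.

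Protocol 10.1 links the sample size to this estimate: "This sample size will allow for assessment of the in-clinic BP and pulse rate on the first day of dosing".

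**The concern.** Because baseline and baseline by time are in the model, each planned analysis behaves like an ANCOVA at each hour on a single pre-dose reading. Under Protocol 5.1.3.1 randomization follows the time 0 check at Visit 3, so both baselines are valid covariates. They carry partly different information: Visit 3 time 0 reflects the subject's level that day, and the Visit 2 reading reflects usual level and the subject's own pattern at that hour. A model that uses one discards whatever the other adds.

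The usual reason for a separate time-matched analysis is to remove the diurnal pattern. For the contrast with placebo, the concurrent placebo arm already removes the part common to all subjects.

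Two unranked models also double the output. Systolic pressure, diastolic pressure and pulse, at 3 doses and 8 post-dose hours, give 3 × 3 × 8 = 72 contrasts with placebo. Two models give 144, without multiplicity adjustment (SAP 6.7) and without a rule for reading a disagreement.

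**Working it through.** **Inputs from the documents.** For the standard deviation, SAP 5.2 says "If the SD of the in-clinic systolic blood pressure (SBP) value is assumed to be 15 mm Hg". 340 subjects are randomized 1:1:1:1, so 85 per arm. The stated distance from the mean to the upper 95% limit is <4.7 mm Hg.

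**Inputs assumed, because the documents give none.** a = correlation of the post-dose reading with Visit 3 time 0, 0.5-0.7. b = its correlation with the Visit 2 matched reading, 0.5-0.6. c = correlation between the two baselines, 0.4-0.6. The SD of 15 is taken as that of an unadjusted reading. Another interpretation would rescale the mm Hg figures but not the percentages.

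**1. The plan's figure.** Half-width = 1.96 × SD × √(2/n) = 1.96 × 15 × √(2/85) = 4.51 mm Hg (4.54 with a t quantile). This meets <4.7 with no baseline adjustment.

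**2. Residual variance at one time point, as a fraction of 15².**
- Visit 3 only: 1 − a²
- Visit 2 only: 1 − b²
- Both: 1 − (a² + b² − 2abc)/(1 − c²)

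The proportional cut from adding the second baseline is then:
- against Visit 3 only: (b − ac)² / [(1 − a²)(1 − c²)]
- against Visit 2 only: (a − bc)² / [(1 − b²)(1 − c²)]

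**3. Extremes over the assumed ranges.** Half-width is 4.51 × √(residual fraction).

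| Comparison | a, b, c | Variance cut | Half-width, mm Hg |
|---|---|---|---|
| Visit 3 only, smallest | 0.7, 0.5, 0.6 | 0.08²/(0.51 × 0.64) = 2% | 3.22 to 3.19 |
| Visit 3 only, largest | 0.5, 0.6, 0.4 | 0.40²/(0.75 × 0.84) = 25% | 3.91 to 3.37 |
| Visit 2 only, smallest | 0.5, 0.6, 0.6 | 0.14²/(0.64 × 0.64) = 5% | 3.61 to 3.52 |
| Visit 2 only, largest | 0.7, 0.5, 0.4 | 0.50²/(0.75 × 0.84) = 40% | 3.91 to 3.03 |

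**4. When the gain disappears.** If b = ac, the Visit 2 reading adds nothing once Visit 3 is known. With a = 0.7, c = 0.6 and b = 0.42 (below the assumed range), the joint model gives 3.22, the same as Visit 3 only. The Visit 2 model gives 4.09.

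**5. Chance disagreement between the two planned estimates.** SD of the difference = 15 × √(2/85) × √(vA + vB − 2k), with vA = 1 − a², vB = 1 − b² and k = 1 − a² − b² + abc. At a = b = c = 0.6: vA = vB = 0.64 and k = 0.496, so the SD is 2.30 × √0.288 = 1.23 mm Hg. It was 1.1 to 1.5 mm Hg across all the correlation sets tried. In 4,000 simulated trials at 0.6, the two estimates differed by more than 1 mm Hg in 41%.

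**6. One answer from one model.** In the same simulations, with both baselines as covariates, the treatment effect agreed to rounding error whether the response was change from Visit 3, change from Visit 2, or the raw reading.

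These calculations treat each hour as an ANCOVA. That matches an unstructured MMRM with complete data for the fixed Visit 3 baseline and approximates it for the time-matched one.

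**The case against.** The strongest reply is that this is an optional efficiency gain. Visit 3 time 0 is same-day and the mean of three seated readings, while Visit 2 lies 11 to 17 days earlier. The Visit 3 model is therefore probably the better single model, and the gain over it may be as little as 2% of variance, or nothing. That stands, and the larger figures against the Visit 2 model should not be read as the expected benefit.

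The endpoint wording (from time 0 on the first day) and the default in SAP 6.2 both lean towards Visit 3 time 0, so one sentence could name a lead without a new model. That also stands in part: it would remove the ambiguity but not recover the precision. The documents lean that way; they do not designate it.

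Two prespecified baseline views are a legitimate safety display, and time-matching informs within-arm profiles that placebo subtraction does not show. This is a reason to keep both models as supportive.

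A joint model needs Visit 2 hourly values, and SAP 6.4 defaults to no imputation. That is a real cost and needs a stated rule. At 7 and 8 hours the Visit 2 covariate is the reused 6-hour value and probably weaker; the by-time terms allow for this.

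A reader might infer that the Day 1 safety assessment is imprecise or that one of the models is biased. The documents support neither: the precision target is met without adjustment, and each model adjusts for a valid pre-randomization reading. Nor do they make the hourly model the principal acute safety result. The Day 1 safety interims in SAP 6.17 use the count of subjects meeting the Day 1 criteria, and the visible text attaches no decision rule to this MMRM.

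**Conclusion.** The point holds as a cheap improvement. The plan uses two separate single-baseline models, no model holds both pre-randomization baselines, and no lead is named. Under the assumed correlations the joint model cuts residual variance by about 2-25% against Visit 3 only and 5-40% against Visit 2 only. In half-width that is about 1-14% and 2-22%. The correlations are assumptions, and outside those ranges the gain over the better single model can be near zero.

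The more practical benefit is one prespecified answer per dose and time point, in place of two that can differ by a millimetre of mercury or more through chance alone.

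**What to change.** In SAP 6.14.7.1, name as the lead Day 1 analysis one MMRM with treatment, time, treatment by time, and both baselines (Visit 3 time 0 and the Visit 2 matched value), each by time. The Visit 2 6-hour value serves at 7 and 8 hours, as already planned. Keep the two single-baseline models as supportive displays.

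Add a rule for a missing baseline: for example, fill a missing Visit 2 hourly value from the subject's other pre-dose readings, without using treatment or post-dose data.

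The cost is SAP wording, one more time-varying covariate and the missing-covariate rule. No new data are needed, and the Day 1 stopping criteria are untouched. SAP Section 3 records that Version 3 was approved after unblinding, so a change made from here on should be labelled as such in the report.

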Home Blood Pressure Monitoring: Home BP measurements will be collected in this study. Blood pressure measurements should be taken twice daily in the seated position using the HBPM equipment provided by Lilly. The subject should be given the HBPM device at Visit 2. Home BP measurements should be conducted for a minimum of 7 days between Visits 2 and 3, for 3 weeks between Visits 3 and 6, and a minimum of 7 days between Visits 10 and 11, and Visits 11 and 801. Home BP should be taken twice in the morning (approximately 1 minute apart) (e.g., 8 AM) immediately following study medication dosing and twice in the evening, approximately 12 hours later (approximately 1 minute apart) (e.g., 8 PM).

All HBPM data will be electronically transmitted to a designated HBPM data processing vendor.

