Change in in-clinic BP and pulse rate from 0 up to 8 hours postdose measured on the first day of study drug dosing will be analyzed using an MMRM analysis with baseline value, treatment, time postdose (hours), and the relevant interaction terms. Two baselines will be considered: the Visit 3 pretreatment value (time 0) and the time-matched baselines from Visit 2 (hourly value 0 to 6 hours). For the second of these, there is no time-matched value for the 7- and 8-hour time points of Visit 3, so the 6-hour time point of Visit 2 will be used as their baseline value. A separate change from baseline analysis will be completed for each baseline approach.

- Change in in-clinic BP and pulse rate from baseline (Visit 2, predrug) up to Week 12 (V11)

Change in in-clinic BP and pulse rate measured at Visit 2 (daily average 0 to 6 hours) to the in-clinic BP and pulse rate measured at Week 6/Visit 8 and Week 12/Visit 11 (daily average 0 to 6 hours) will be analyzed by an MMRM model with baseline value, treatment, and the relevant interaction terms. Analysis at 6 weeks will help to evaluate any significant changes (if any) in BP and pulse rate earlier than 12 weeks (end of study) and if they accommodate by 6 weeks.

- Daily average change in home BP measurements and pulse rate from baseline to Week 12.

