6.14.7.2. Tertiary/Exploratory Safety Analyses

The following exploratory safety endpoints will also be analyzed using an MMRM model adjusting for baseline reading:

- daily average change in HBPM measurements and PR from baseline to Week 12
- change in MDS-UPDRS items 4.1 and 4.2, time with dyskinesias, and impact of dyskinesias
- change in item 1.2 (hallucinations/psychosis) score of the MDS-UPDRS Part IA from baseline to Week 12
- change in score for the delusion (Part A) and hallucinations (Part B) domains of the NPI from baseline to Week 12
- change in QUIP score from baseline to Week 12, and
- change in PWC-20 total score will be analyzed using an analysis of covariance (ANCOVA) model with a covariate for baseline score. The primary analysis will be a change from baseline (Visit 11) to the in-person follow-up visit (Visit 801).

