6.14.7.3. Home Blood Pressure Monitoring Analyses

Change from baseline in (i) average daily, (ii) morning, and (iii) evening home BP and PR to Week 3 will be analyzed using an MMRM with fixed effects for baseline value, treatment, day, and treatment by day and baseline by day interaction terms with repeated measures of day within subject. The baseline value for each analysis will be defined as the average of all relevant samples taken prior to first dose of LY3154207. A similar analysis will be completed for the 7 days before and after last dose. The MMRM analysis of the HBPM will provide daily estimates of change from baseline for the first 3 weeks of treatment. If there is a rise in BP and PR, the duration taken to accommodate can be assessed using the daily estimates of change from baseline. Visualizations will be used to characterize the temporal course of BP and PR changes, including accommodation. Additional exploratory analyses may be considered as necessary to further characterize the cardiovascular effects of LY3154207.

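### Accommodation of a Day 1 BP or pulse rise: the in-clinic models give the effect at each time, but no estimate or interval for the change in effect

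*SAP*

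**What the plan says.** Protocol 10.1 says that after any initial rise in BP or pulse, "the in-clinic 6- and 12-week assessments along with the HBPM measure will be used to assess if the rise accommodates". SAP 5.2 repeats the aim, adds ABPM, and says these "measures will be used to assess whether the rise accommodates". SAP 6.14.7.1 gives the Week 6 in-clinic analysis the same purpose: changes "in BP and PR earlier than 12 weeks (end of study) and if they accommodate by 6 weeks".

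Two in-clinic models follow.

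- **Day 1.** Visit 3 only, hours 0 to 8, with hour as the repeated factor. It is run once against Visit 3 Time 0 and once against time-matched Visit 2 values.
- **Weeks 6 and 12.** The response is the 0-6 h daily average as change from Visit 2, with visit as the repeated factor. SAP 6.14.7.1 does not list the visit levels. Protocol 10.3.4.3 names "in-clinic BP and pulse rate measured at Week 6/Visit 8 and Week 12/Visit 11" and not Visit 3.

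Under SAP 6.2, every MMRM reports differences from placebo with 95% intervals.

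Outside the in-clinic data, SAP 6.14.7.3 models home readings to give "daily estimates of change from baseline for the first 3 weeks of treatment" and repeats this around the last dose. SAP 6.14.7.2 lists "daily average change in HBPM measurements and PR from baseline to Week 12" as exploratory. SAP 6.14.7.4 fits one MMRM across the ABPM periods, in addendum subjects only.

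**The concern.** Accommodation is a change in treatment effect: the drug-placebo difference on Day 1 compared with the same difference at Week 6 or 12. Neither in-clinic model contains both times, so neither can produce that contrast or its standard error. Subtracting one output from the other gives a point estimate, most naturally from the Day 1 run that uses Visit 2 as reference, but no planned interval.

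The stake is the reading of a safety question the sponsor set itself. If Day 1 is significant and Week 6 is not, a reader may conclude that the rise has faded. Under the protocol's own later-visit SD, a constant 4 mm Hg effect with no accommodation would be non-significant at Week 6 in 35.5% of trials (SD 10, 68 per arm; the 4 mm Hg is assumed).

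**Working it through.** **Inputs from the documents (Protocol 10.1 and 5.1).** 340 randomised 1:1:1:1, so 85 per arm; 20% discontinuation, so 340 × 0.8 / 4 = 68 per arm later. SD is 15 mm Hg for Day 1 SBP and 10 mm Hg for average SBP at the later visits.

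**Assumed, not in the documents.** Correlation rho between the Visit 3 and later changes of 0.3 to 0.7; a 5 mm Hg change in effect for power; and SD 10 for a Visit 3 average, in the rows that use it.

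**The plan's own figures.** Half-width = 1.96 × SD × sqrt(2/n).
- Day 1: 1.96 × 15 × sqrt(2/85) = 4.51, consistent with the stated <4.7.
- Weeks 6/12: 1.96 × 10 × sqrt(2/68) = 3.36, consistent with the stated <3.5.

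Both reproduce. Each is the precision of an effect at one time, not of a change in effect.

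**Change in effect, results treated as independent.** 1.96 × sqrt(2·s3²/85 + 2·s8²/68), where s3 and s8 are the SDs at Visit 3 and the later visit. This gives 4.51 for SDs 10/10 (equal to the Day 1 figure by coincidence) and 5.62 for 15/10.

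**Change in effect, one model, 68 per arm with both visits.** 1.96 × sqrt(2·(s3² + s8² − 2·rho·s3·s8)/68). For example, with SDs 10/10 and rho 0.5 the SD of the difference is sqrt(100 + 100 − 100) = 10, and the half-width is 3.36.

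| SBP, each dose vs placebo | rho 0.3 | rho 0.5 | rho 0.7 | Independent |
|---|---|---|---|---|
| Half-width, SD 10/10 | 3.98 | 3.36 | 2.60 | 4.51 |
| Power for 5 mm Hg, SD 10/10 | 69% | 83% | 96% | 58% |
| Half-width, SD 15/10 | 5.15 | 4.45 | 3.60 | 5.62 |
| Power for 5 mm Hg, SD 15/10 | 48% | 60% | 78% | 41% |

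A likelihood-based MMRM also uses the other 17 Visit 3 values per arm. The variance per arm becomes s3²/85 + s8²(1 − rho²)/68 + rho²·s8²/85 − 2·rho·s3·s8/85. The half-widths are then 3.84, 3.28 and 2.56 (SD 10/10) or 4.83, 4.18 and 3.40 (SD 15/10).

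At rho 0 the gain disappears. With SD 10/10 the 68-per-arm figure is 4.75, and the likelihood version equals 4.51. The relevant rho is the one left after baseline adjustment.

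**Choice of hours.** Time 0 precedes dosing at Visits 3, 8 and 11 (Protocol Section 2, footnote g), but only at Visit 3 has the subject had no drug. A constant 5 mm Hg post-dose effect averages 5 × 6/7 = 4.29 over the seven Visit 3 readings. If that effect is fully present pre-dose at Visit 8, a 0-6 h contrast shows 5/7 = 0.71 with no true change; over hours 1-6 it shows 0.

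Dropping Time 0 costs little. Assume a between-day SD of 5.5, an hourly SD of 9, and Time 0 as the mean of three readings. The variance of a visit average is 5.5² + 9²/6 = 43.75 for hours 1-6, and 5.5² + (6 × 9² + 9²/3)/49 = 40.72 for 0-6 h. The standard error ratio is sqrt(43.75/40.72) = 1.04.

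**The case against.** The documents assign accommodation to a package, not to the in-clinic visits alone. The home-monitoring model has treatment-by-day terms, its daily estimates are meant to show how long accommodation takes, and SAP 6.14.7.3 adds visualisations and leaves room for further exploratory analyses. So a reader who infers that accommodation is not analysed goes too far.

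Nor is the in-clinic comparison left to the eye. Each time has a model-based effect with a 95% interval, and the later interval bounds any residual rise to within 3.36 mm Hg. The Week 6 test has about 83% power for a persisting 5 mm Hg effect (SD 10), the same as the linked contrast at rho 0.5. Because the SAP lists no visit levels, one might also argue that Visit 3 is not excluded.

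These points limit the concern but do not remove it.

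- Home readings are taken in the morning "immediately following study medication dosing and twice in the evening, approximately 12 hours later", so they do not follow the hours after the dose as the clinic profile does. None is scheduled between Visits 6 and 10, which includes Week 6. Under SAP 6.12.7, vital signs at telephone visits came from the home device, but no accommodation analysis is specified for those values.
- ABPM does use one linked model for this question, but only in addendum subjects.
- On visit levels, the protocol names only Visits 8 and 11, and neither document writes a contrast with Visit 3.
- A bound on the Week 6 effect answers a different question from how far the effect fell.

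A further inference is that antihypertensive changes, which Protocol 7.7 allows, will disguise a persisting rise. The documents do not establish this. Concomitant medications are already to be summarised by arm (Protocol 10.3.2.4, SAP 6.10), and the size of any such effect cannot be derived.

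**Conclusion.** The gap is real and narrow. The in-clinic plan estimates the treatment effect on Day 1 and at Weeks 6 and 12, but not the change between them, although those visits are meant to help show accommodation. HBPM and ABPM give partial evidence and do not estimate the change in post-dose in-clinic effect.

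The absence of the contrast is certain from the text. The size of the gain is not. It depends on an assumed correlation and, for power, an assumed 5 mm Hg change, and power is materially lower throughout with the protocol's Day 1 SD of 15.

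Subjects who meet the Day 1 stopping rules (Protocol 5.1.3.1 and 8.1.1) contribute Day 1 data only. Setting separate models side by side therefore mixes accommodation with a change in who is observed. A joint model keeps their Day 1 values but rests on missing at random.

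This is worth considering, as an improvement to a secondary safety analysis in an exploratory study.

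**What to change.** Add Visit 3 as a response level in the Visit 8/11 MMRM. Use the hours 1-6 average as response and the Visit 2 hours 1-6 average as baseline. Report the Visit 8-minus-Visit 3 and Visit 11-minus-Visit 3 treatment contrasts with 95% CIs, for BP and pulse, as the in-clinic accommodation estimate. Keep the planned 0-6 h analysis.

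State that subjects discontinued under the Day 1 stopping rules contribute Day 1 data only, and that the contrast assumes missing at random.

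The cost is SAP wording, one extra response level and two contrasts per variable; the readings are already scheduled. The hours 1-6 average raises the standard error by about 4% under the variances assumed above. SAP Version 3 was approved after unblinding (SAP Section 3), so an analysis added now should be labelled post hoc.

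As a separate option, count antihypertensive starts and dose increases by arm, and run one sensitivity analysis that sets BP after such a change to missing. It too assumes missing at random, and it should sit beside the as-observed result, not replace it.
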